7.3 Informed Consent

The investigator or authorized delegate will explain the nature of the planned treatment and objectives of the study to a patient (or patient's legally authorized representative). The investigator or authorized delegate will allow adequate time for the patient or legal representative to read and review the consent form and to ask questions.

The patient (or the patient's legally authorized representative) and the investigator (or authorized delegate) will sign and date the Institutional Review Board (IRB)-approved ICF. The original signed ICF form will be retained in the subject's study records. A copy of the signed ICF will be provided to the subject (or legal representative) and a copy placed in the subject's medical records.

The investigator or authorized delegate must document in the subject's medical records that the subject was consented and the date on which the consent was obtained, and that a copy of the signed ICF was given to the subject.

7.4 Point of Enrollment and Numbering of Study Subjects

A patient will be considered enrolled as a study subject when they have met all study eligibility criteria and have signed the informed consent form (or their legally authorized representative has signed). The study database will assign the subject number. At the time of subject enrollment, the investigator or other study team member will notify the contract research organization (CRO) via fax or email.

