7.2 Screening

Screening is defined as the process of reviewing a patient's medical records against the study eligibility (inclusion and exclusion) criteria to determine if the patient is eligible to enroll in the study. It is expected that the medical records will contain adequate information to determine if a patient meets most of these criteria. If a patient meets most of the eligibility criteria, they can be consented for the study. If a patient is not consented they are considered a screening failure. Screening failures will be tracked on a Screening and Enrollment Log.

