10.1.1 Primary Endpoint: Analysis of Adverse Events

For adverse events, both event counts and counts of subjects experiencing those events will be reported in tabular summaries. Rates will be reported based on the number of subjects experiencing one or more event as a proportion of all enrolled subjects and these subject rates will serve as the primary analysis.

Adverse event analysis may be repeated for events that occur after the initiation of treatment with rates calculated as a proportion of treated subjects, if it occurs that not all enrolled subjects undergo treatment with LITT.

Event counts, subject counts, and subject rates will also be reported for the following subsets of adverse events: SAE, SADE, UADE, USADE. Adverse events will be further characterized by tabulating the event severity and relationship (see section 9.1).

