10.2.2 Analysis Populations

All subjects enrolled in the study (including those withdrawn from the investigation) will be accounted for and documented.

The following analysis populations are defined:

Enrolled Set: All subjects enrolled in the study

Treated Set: All subjects that initiate treatment with LITT (received thermal delivery with the NBS)

Per-protocol Set: All subjects in the Treated Set that are treated according to the protocol requirements and meet study and treatment eligibility criteria

In the feasibility study setting, conclusions about performance are best informed by analyses of the Treated Set. Analyses may be repeated on the Enrolled Set for full reporting of study results and on the Per-protocol Set to provide insight into the potential impact of protocol deviations on the analysis results.

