Up to 45 subjects will be enrolled at up to 8 sites in the United States to ensure that approximately 30 subjects undergo the LITT procedure. It is expected that each site will enroll no more than 10 subjects to ensure that all sites have an opportunity to contribute data to the study and to prevent any one site from having an outsized influence on the overall results of the study.

10 Analysis Populations

The following analysis populations are defined:

- **Enrolled Set:** All subjects enrolled in the study
- **Treated Set:** All subjects that received thermal delivery with the NBS
- **Per-protocol Set:** A subset of the Treated Set that does not have a protocol deviation (see below)

In the feasibility study setting, conclusions about performance are best informed by analyses of the Treated Set. Analyses may be repeated on the Enrolled Set for full reporting of study results and on the Per-protocol Set to provide insight into the potential impact of protocol deviations on the analysis results.

The Per-protocol Set will exclude subjects with protocol deviations that seriously affect the integrity of the data. The deviations that will result in subject data being excluded from the Per-Protocol Set are:

1. Subject did not meet the following study inclusion criteria:

- Diagnosis of unilateral medial temporal lobe epilepsy (MTLE) confirmed clinically and with either (1) ictal scalp recording and MRI evidence of mesial temporal sclerosis or (2) intracranial ictal onset consistent with hippocampal origin.
- Subject or legally authorized representative is able to provide appropriate consent to participate.
- Subject averages 3 or more complex partial seizures (with or without secondary generalization) per month over the 3 most recent consecutive months prior to baseline.

2. Subject should not have undergone the study procedure (i.e. subject was found not to have met the treatment eligibility criteria in Section 6.4 of the clinical study protocol)

Protocol deviations may be reviewed prior to performing analysis of study outcomes to identify deviations, in addition to those identified above, that may result in excluding a subject from the per-protocol set. Reviewing protocol deviations prior to analysis of outcomes is intended to prevent bias in the analysis results while still allowing for identification of significant protocol deviations that could impact outcomes but that were not anticipated at the time that the Statistical Analysis Plan was written.

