11.1.1 Primary Endpoint: Analysis of Adverse Events

Adverse events will be presented in summary tables displaying the number of events, the number of enrolled subjects with ≥ 1 event, and the proportion of enrolled subjects with ≥ 1 event. The rates of adverse events will serve as the primary analysis.

Adverse event analysis may be repeated for only those events that occur after the initiation of treatment with rates calculated as a proportion of treated subjects..

Phase

The timing of adverse events relative to the initial LITT procedure will be tabulated by reporting the event counts, subject counts, and subject rates of events that occur within the following phases:

- **Baseline:** Prior to LITT procedure
- **Operative:** From the beginning of the LITT procedure through 30 days post-procedure
- **Year 1:** From 31 days post-procedure through 12 study months (12 month visit date or close of 12 month visit window if 12 month visit is missed)
- **Year 2:** After 12 study months through 24 study months (24 month visit date or close of 24 month visit window if 24 month visit is missed)

Additional analyses may be performed that divide the above phases into more detailed time intervals or that combine phases to present an overall summary of all adverse events through a specific time point (e.g. Operative Through Year 2).

Severity

The severity of adverse events will be tabulated by reporting the event counts, subject counts, and subject rates of events that are:

- **Mild:** Does not interfere in a significant manner with the subject's normal functioning level.
- **Moderate:** Produces some impairment of functioning but is not hazardous to health.
- **Severe:** Produces significant impairment of function or incapacitation and is a hazard to the subject's health.

Relationship

The relationship of adverse events to the device treatment or procedure will be tabulated by reporting the event counts, subject counts, and subject rates of events based on the following relationship categories:

- **Definite** – The adverse event follows a strong temporal sequence to the receipt (or attempted receipt) of the device treatment or procedure. This can include an adverse event that occurs after the study procedure.

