12.2 Disposition of Subjects

All subjects that sign the informed consent form (ICF) will be accounted for by reporting

1. Number of subjects that sign the ICF/enroll
2. Number of subjects that enroll and meet all eligibility criteria
3. Number of subjects that are eligible for treatment (complete the Baseline Phase and meet the treatment criteria)
4. Number of subjects that exit the study prior to LITT treatment
5. Number of subjects that undergo LITT treatment
6. Number of subjects that complete each follow-up visit
7. Number of subjects that exit the study after LITT treatment but prior to the Month 24 visit.

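### Protocol 7.4 and SAP 12.2 define enrolment differently, so the primary adverse-event rate has two possible denominators whenever a consented subject proves ineligible

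*Protocol*

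**What the plan says.** **Definition of enrolment.** Protocol 7.4 sets two conditions: "A patient will be considered enrolled as a study subject when they have met all study eligibility criteria and have signed" the consent form. SAP 12.2 lists as its first disposition count "Number of subjects that sign the ICF/enroll" and as its second "Number of subjects that enroll and meet all eligibility criteria". Under the protocol definition those two counts could never differ, so the SAP list makes sense only if an ineligible subject can be enrolled.

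**Where the term is used.** Protocol 10.1.1 calculates adverse-event rates "as a proportion of all enrolled subjects and these subject rates will serve as the primary analysis". SAP 11.1.1 reports "the proportion of enrolled subjects with ≥ 1 event. The rates of adverse events will serve as the primary analysis". Protocol 10.2.2 defines the population as "Enrolled Set: All subjects enrolled in the study", and SAP 10 uses the same phrase, "All subjects enrolled in the study". Neither says which meaning of enrolled applies.

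**Failure after consent.** Protocol 7.2 permits consent once most criteria are met. The footnotes to 6.3.1 and 6.3.2 allow some criteria to be checked after consent. The pregnancy test and the IQ criterion are tied to the Baseline visit. On screening failures, 7.2 says "If a patient is not consented they are considered a screening failure"; it names no category for a patient who consents and is then found ineligible.

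**Versions.** SAP 3 cites protocol Rev A, and the current protocol is Rev B. SAP 2 notes that protocol changes may require the SAP to be updated.

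**The concern.** The primary safety result is a proportion, and the two documents do not agree on who belongs in its denominator. A subject who signs the form and then fails the IQ or pregnancy criterion is enrolled under SAP 12.2 and not enrolled under protocol 7.4. Two analysts, each following one document, would report different primary rates from the same events.

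The discrepancy also has a direction. Protocol 9.1 starts adverse-event collection on the day of the procedure. A consented, ineligible subject who never reaches the procedure cannot contribute an event but is counted under the SAP wording. That makes the device look safer for a reason unrelated to its performance. If the definition is left open until data are in hand, the denominator could be chosen with the events already known.

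**Working it through.** **Inputs**

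- Operated subjects: about 30 (protocol 6.1; SAP 9).
- Ceiling on enrolment: 45 (SAP 9 only; protocol Rev B gives no such figure).
- Adverse-event collection starts on the procedure day (protocol 9.1).
- Number consented, found ineligible and not operated on, *k*: not given in either document, so a range is assumed.
- Subjects with at least one event, *x*: 9, assumed for illustration.
- Interval method: Clopper-Pearson, as named in SAP 12.1.

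**Step 1: the plan's own figure.** Protocol 10.2.4 and SAP 9 state roughly an 80% chance of seeing an event of 5% per-subject probability at least once in 30 subjects. 1 − 0.95^30 = 0.785, which agrees and is not in dispute. The figure of 30 is the number operated on, whereas the primary rate is divided by the number enrolled.

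**Step 2: the two rates.** Let *E* be the number consented and eligible.

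- Protocol 7.4: rate = *x* / *E*.
- SAP 12.2: rate = *x* / (*E* + *k*).
- Ratio of SAP to protocol = *E* / (*E* + *k*). This equals 1 when *k* = 0 and is below 1 otherwise.

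The one-way direction needs two conditions: the *k* subjects are not operated on, and no pre-procedure events are counted. Protocol 9.1 supplies the second. SAP 11.1.1 tabulates a phase before the procedure, which does not match that rule.

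**Step 3: small case.** Every eligible subject is operated on, so *E* = 30.

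| *k* | SAP rate |
|---|---|
| 0 | 9/30 = 30.0% |
| 1 | 9/31 = 29.0% |
| 2 | 9/32 = 28.1% |

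The protocol rate is 30.0% throughout.

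**Step 4: larger case, assumed.** 45 sign the form and 36 to 40 of them meet all criteria, so *k* is 5 to 9.

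| Denominator | Rate | 95% CI |
|---|---|---|
| SAP 12.2 | 9/45 = 20.0% | 9.6 to 34.6% |
| Protocol 7.4, *E* = 40 | 9/40 = 22.5% | 10.8 to 38.5% |
| Protocol 7.4, *E* = 36 | 9/36 = 25.0% | 12.1 to 42.2% |

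The difference is 2.5 to 5 percentage points.

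**Step 5: outer bound.** If all 15 subjects between 30 and 45 were consented but ineligible, the ratio would be 30/45 = 0.67, that is 9/30 = 30% against 9/45 = 20%. This overstates the definitional effect, because the 15 also include eligible subjects who are not operated on, and those are enrolled under both definitions.

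**Step 6: what a common definition leaves.** In the larger case, adopting protocol 7.4 gives 22.5% to 25%, while the rate among the 30 operated is 30%. The remaining gap is 5 to 7.5 points and comes entirely from eligible but unoperated subjects.

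**The case against.** The strongest reply is that the effect may be very small. Protocol 7.6.1 expects medical records to show whether a patient meets the criteria, so few may fail after consent. The ceiling of 45 belongs to a SAP whose visit schedule runs from Week -12 to Week 0, whereas Rev B has a single Baseline visit. There are no hypothesis tests, both documents say conclusions about performance are best informed by the Treated Set, and counts are reported alongside rates so that a reader could recalculate. The mismatch is probably version drift. All of this stands and limits the size. It does not remove the conflict: the treated-subject rate is only optional in both documents, and the primary rate is still stated on enrolled subjects.

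Three stronger readings are tempting and are not supported.

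- *Subjects who fail after consent vanish from the accounts.* SAP 12.2 undertakes to account for everyone who signs the form, and its first count minus its second is exactly this group. Protocol 7.2 calls unconsented patients screening failures but does not say that only they are.
- *Protocol Table 1 is circular, because Baseline is timed from an enrolment that needs Baseline results.* The window is within 7 days of enrolment, not after it, so assessments in the preceding days can satisfy it. Neuropsychological testing from the prior 6 months may be used, and the table's header row is visibly disordered in the extracted text.
- *The wording by itself shifts the rate by 2.5 to 5 points.* That range comes from assumed counts.

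**Conclusion.** The concern holds in a limited form. The two documents give different definitions of the denominator of the primary adverse-event rate, and neither Enrolled Set definition settles which applies. The rates differ only if at least one consented subject fails a criterion, an event the protocol foresees but does not quantify. For such subjects who are not operated on, and with events collected from the procedure day, the SAP wording can only lower the rate.

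A plausible size is 1 to 2 points (30% to 29% or 28%) if one or two subjects are involved. Larger effects need assumed numbers, and dilution by 30/45 is an upper limit that includes other causes. Nothing here invalidates the study, but the definition should be settled before the first analysis. Aligning it does not make the enrolled rate a good measure of risk in operated subjects; the treated-subject rate is needed for that.

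**What to change.** 1. **SAP 12.2 and SAP 10.** Adopt the protocol 7.4 meaning: enrolled is eligible and consented. Let the first disposition line count signers of the consent form only. List consented but ineligible subjects on a separate line as screening failures after consent, excluded from the Enrolled Set.
2. **Protocol 7.2.** Extend the screening-failure wording to patients who consent and are then found ineligible.
3. **Protocol 10.1.1 and SAP 11.1.1.** Change the treated-subject adverse-event rate from optional to mandatory, since eligible but unoperated subjects dilute the enrolled rate under any definition.
4. **Optional.** Time the Baseline visit in protocol Table 1 from consent, as a clarification.

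Defining enrolment by consent alone in both documents would be equally consistent, but it would keep subjects with no chance of an event in the primary denominator. The cost is wording in two documents, with no new data, visits or subjects. The SAP needs updating to Rev B in any case.

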7.5 Schedule of Visits and Testing Requirements

Table 1 and Table 2 outline the visits, visit windows, and testing requirements at each evaluation time point.

Table 1: Visits and Testing Requirements and Data Collection Summary (Baseline through Month 12)

Visit Window	Baseline			LITT Proc.	DC	Post-Procedure												
	Within 7 days of enrollment	Day of DC	Within 30 days of Baseline ¹			Day 14	Mo. 1	Mo. 2	Mo. 3	Mo. 4	Mo. 5	Mo. 6	Mo. 7	Mo. 8	Mo. 9	Mo. 10	Mo. 11	Mo. 12
	Visit Type	Icon 1	Icon 2	Icon 3	Icon 4	Icon 5	Icon 6	Icon 7	Icon 8	Icon 9	Icon 10	Icon 11	Icon 12	Icon 13	Icon 14	Icon 15	Icon 16	Icon 17
Inclusion and exclusion criteria	✓																	
Informed consent	✓																	
Demographics	✓																	
Medical, surgical & epilepsy history	✓																	
QOLIE-31	✓													✓				✓
Medication review (epilepsy and non-epilepsy)	✓					✓	✓	✓	✓	✓	✓	✓	✓	✓	✓	✓	✓	✓
Physical exam	✓						✓	✓						✓				✓
Neurological exam	✓						✓	✓	✓				✓			✓		✓
Formal visual field testing	✓													✓				
Serum pregnancy test (if female of child-bearing potential)	✓																	
Neuropsychological testing ²	✓ ³												✓		✓			✓
Functional assessment	✓							✓	✓				✓		✓		✓	✓
Seizure classification assessment	I												U		U			U
Seizure diary	T					T/D	C/D	C/D	C	C/D	C	C	C/D	C	C	C/D	C	C/D
Adverse event monitoring						✓	✓	✓	✓	✓	✓	✓	✓	✓	✓	✓	✓	✓
Treatment criteria																		
LITT treatment						✓												
MRI						✓	✓ ⁴							✓				
Surgical pain VAS						✓	✓							✓		✓		✓
Surgical outcome classifications ⁵													✓		✓			✓
Subject satisfaction													✓					✓

Abbreviations: C, collect; D, dispense; DC, discharge; I, initial; LITT, laser interstitial thermal therapy; Mo., month; MRI, magnetic resonance imaging; proc., procedure; QOLIE-31, Quality of Life in Epilepsy - 31; T, training; U, update; VAS, visual analog scale.

¹ Surgery may be performed >30 days after the Baseline Visit if needed to accommodate neuropsychological test scheduling.

² See Appendix C for details of the neuropsychological testing at each visit. These can be performed on a separate day than the Baseline visit.

³ Prior neuropsychological testing may be used for Baseline if the testing was conducted within 6 months prior to the Baseline visit and there were no significant changes to the subject's AEDs or changes to the subject's clinical condition that may affect cognitive function.

⁴ The MRI performed at the end of the LITT procedure may be used as the Discharge Visit MRI.

⁵ See Appendix D for details about the Engel and ILAE surgical outcome classifications.

Table 2: Visits and Testing Requirements and Data Collection Summary (Month 12 through Month 24)

Visit Window	Months 13, 14, 15, 16, & 17	Month 18	Months 19, 20, 21, 22, & 23	Month 24	Early Withdrawal
	± 7 days	± 14 days	± 7 days	± 14 days	
Visit Type					
QOLIE-31		✓		✓	✓
Medication review (epilepsy and non-epilepsy)	✓	✓	✓	✓	
Neurological exam		✓		✓	✓
Functional assessment		✓		✓	✓
Seizure diary	C/D	C/D	C/D	C	✓
Adverse event monitoring	✓	✓	✓	✓	✓
Surgical outcome classifications ¹		✓		✓	✓
Subject satisfaction		✓		✓	✓
Neuropsychological testing ²					✓

Abbreviations: C; collect; D, dispense; QOLIE-31, Quality of Life in Epilepsy - 31; U, update.

¹ See Appendix D for details about the Engel and ILAE surgical outcome classifications.

7.6 Procedures and Subject Assessments

7.6.1 Baseline Visit

Prior to consenting patients for the study, Site personnel will evaluate potential candidates by reviewing the patient medical records against the study eligibility criteria. It is expected that the medical records will contain adequate information to determine if the patient meets these criteria. Potential patients will be asked to complete the informed consent process.

The following evaluations and assessments will be performed at this visit:

- Demographics
- Medical, surgical and epilepsy history
 - Epilepsy history will include collection of 12 months of retrospective seizure frequency data; data from the 3 months prior to the Baseline visit will be used for eligibility determination. See Appendix B for more details.
- Quality of Life in Epilepsy - 31 (QOLIE-31). It is preferred that the subject completes the questionnaire prior to any other baseline tests.
- Medication review, including collection of 12 months of retrospective epilepsy medication data (as available) to qualitatively assess medication stability prior to the NeuroBlate procedure. See Appendix A for more details.
- Physical exam
- Neurological exam
- Visual field testing (automated perimetry)
- Serum pregnancy test (if female and of childbearing potential)
- Neuropsychological testing (see Appendix C).
- Functional assessment (including employment status, education, living arrangements, driving status)
- Seizure classification assessment
- Seizure diary training

7.6.2 LITT Procedure

An MRI will be performed prior to surgery to determine trajectory and frame/arc settings. The LITT procedure will be performed per the IFU. Adverse events that occur during the procedure will be collected.

Postoperatively, the subject should be managed per the institution's standard of care for subjects receiving LITT. This includes monitoring of the subject's neurological status as it relates to possible intraoperative or postoperative adverse events (including intracranial hemorrhage).

Subjects experiencing a failed LITT treatment attempt (stopping the procedure prior to thermal delivery) will be followed for 1 month post-procedure for adverse events.

7.6.3 Discharge Visit

Prior to hospital discharge the following evaluations and assessments will be performed:

- Medication review (see Appendix A)
- Physical exam
- Neurological exam
- Adverse event monitoring
- MRI (the MRI performed at the end of the LITT procedure can be used as the Discharge Visit MRI).
- Surgical pain visual analog scale (VAS)
- Seizure diary training refresher and dispensing (see Appendix B)

7.6.4 Day 14 Visit

The following evaluations and assessments will be performed at this visit:

- Medication review (see Appendix A)
- Functional assessment (including employment status, education, living arrangements, driving status)
- Seizure diary collection and dispensing (see Appendix B)
- Adverse event monitoring
- Surgical pain VAS

